Clinical Optimization of Ambient Temperature and Heating Methods in Caring in Major Burns Patients

Optimal Heating Temperature in Major Burns Patients

MSN [name]

Universitat Rovira i Virgili
Sanidad Castilla y León
Hospital Universitario Rio Hortega Valladolid
Universidad de Valladolid
[contact]

Study Protocol, Statistical Analysis Plan (SAP), Informed Consent Form (ICF)

Version 1.0

Marchy, 2020

HeatingBurns01- Study Protocol, Statistical Analysis Plan (SAP), Informed Consent Form (ICF)

1. Material and methods

6.1 Design, methodology and justification:

Pre-experimental pre-experimental epidemiological study without control group, in large burnt patients that will evaluate the influence on the metabolic expenditure of the inclusion of active external overheating in the control of ambient temperature adjusted to thermal comfort.. Two methods of active external heating, thermal plate and convective air blanket shall be used. Metabolic expenditure shall be measured by indirect calorimetry in the usual treatment with passive external overheating and post-intervention in the combination of passive and active external warming.

Sand pre-study the combination of passive and active external overheating by measuring the operating temperature in various cases for optimal application, as well as the definition of thermal comfort in the unit of large burns. In this way, two study stages are integrated as shown in *Table 5.*.

Table 5: Study stages Clinical optimization of ambient temperature and heating methods in the care of the patient large burned according to thermal comfort

Stage 1	Stage 2
Empirical study of operating temperature according to the	Quasi-experimental study of large burned patients to study
combination of passive and active external heating methods for the definition of environmental comfort.	the impact on metabolic expenditure of the inclusion of active external overheating in environmental temperature
methods for the definition of environmental connoct.	control

6.2. Population and sample:

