6.2.4. Sample size

Using the GRANMO sample matingc, Version 7.12 was calculated for the difference of media coupled in energy expenditure at rest of the combination of passive and active external (in two methods, by thermal plate and convective air blanket) versus passive external heating.

Accepting an alpha risk of 0.05 and a beta risk of 0.2 in a bilateral contrast, 34 subjects are required to detect a difference equal to or greater than 0.15 units. A standard deviation of 0.3 is assumed. A 5% tracking loss rate has been estimated.

The difference expected to be found in the resting metabolic expenditure rate of at least 0.1 times the GMB. The increase in baseline metabolic expenditure of these patients in studies with burned patients was 1.4 times with standard deviation of 0.2 - 0.32 times. The sample will be adjusted to the standard deviation values presented in the pilot sample.

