6.5. Data analysis

The values of the temperatures measured in the empirical study, the discrete and absolute variables according to descriptive in ranges, maximum and minimum, trend, mean and median valuesshall berecorded.. The VMP and PPI values willbe calculated through the software associated with the Testo® measuring instruments.

A descriptive analysis of the variables obtained shall be carried out. Continuous quantitative variables shall be analysed by the Kolmodorov-Smirnov test and described as mean standard deviation (DS) in case of normal distribution, or as median and range if the distribution does not follow the normal distribution. Qualitative variables shall be described by absolute and relative frequencies. A single-rate analysis shall be performed by observing as variables main dependent temperature and metabolic expenditure. With a 95% confidence interval (p<0.05) quantitative variable means will be contrasted using Student t or Mann-Whitney's U-depending on the sample distribution. The Chi-square test for contingency tables and the Fisher test will be used to assess association of qualitative variables.

A logistic regression model may be established based on the results, analyzing the strength of association in explanatory and predictive terms.

IBM SPSS Stadisticssoftware® v.23 will be used for statistical data analysis

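### Section 6.5 does not carry over the paired basis of the sample size: it names Mann-Whitney U for same-patient data, leaves Student t unspecified, and does not define the device contrast or contrasts

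*Combined protocol and SAP*

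**What the plan says.** **Sizing (6.2.4).** The sample size "was calculated for the difference of media coupled in energy expenditure at rest"; the word translated as coupled means paired. The comparison is of passive plus active heating ("in two methods, by thermal plate and convective air blanket) versus passive external heating"). The risks are set by "Accepting an alpha risk of 0.05 and a beta risk of 0.2 in a bilateral contrast". The difference is 0.15, the SD 0.3, the loss rate 5% and the result 34 subjects. The same section says the sample will be adjusted to the SD seen in the pilot.

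**Measurement (6.2.3, 6.4.2).** Each patient is assessed under all three conditions, on three consecutive nights.

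**Contrast (6.1).** Energy expenditure is measured "in the usual treatment with passive external overheating and post-intervention in the combination of passive and active external warming". Like the text in 6.2.4, this can be read as one pooled active-versus-passive comparison or as one comparison per device.

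**Analysis (6.5).** The univariate analysis proceeds by "observing as variables main dependent temperature and metabolic expenditure. With a 95% confidence interval (p<0.05"), and "quantitative variable means will be contrasted using Student t or" Mann-Whitney's U, depending on the distribution. No paired test is named, no contrast is defined and no rule for more than one test is given.

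**The concern.** The data are repeated measurements on the same patients, and the sample size relies on that. Mann-Whitney U ignores the pairing, so whenever the data are judged non-normal the test named in 6.5 does not match the design. For normal data the text leaves the analyst to decide whether Student t is paired.

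If nights are positively correlated within a patient, an independent-samples test uses too large a standard error. Its true error then falls below the nominal 5%, and part of the power that 6.2.4 planned for is lost.

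The undefined contrast is a second gap. A pooled test and two device tests answer different questions. Without a declared choice, and with temperature named beside metabolic expenditure, the comparison that carries the conclusion could be chosen after the data are seen.

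**Working it through.** **Inputs.** From 6.2.4: two-sided alpha 0.05, power 80%, difference 0.15, SD 0.3, loss 5%. Assumed: between-night correlation r within a patient, equal for all pairs of nights, with equal variances. The documents give no r; 0.5 is used for illustration and a range is shown.

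**1. Reproducing 34.** n = [0.3 × (1.960 + 0.842) / 0.15]² = 31.4, so 32 evaluable; 32 / 0.95 = 33.7, so 34. This works with 0.3 as the SD of the paired difference. The independent-groups formula with 0.3 as the SD of a single measurement gives 63 per group. The plan's figure is therefore a paired one. By the exact paired t, power is 78.2% at 32 evaluable (80.7% by normal approximation).

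**2. Independent-samples test on these data.** Hold the paired-difference SD at 0.3.
- Single-night SD: s = 0.3 / √[2(1 − r)].
- True standard error of the mean difference: 0.3 / √32 = 0.0530.
- Standard error the test uses: s × √(2/32) = 0.25s.
- Power ≈ Φ[(0.15 − 1.96 × 0.25s) / 0.0530].
- Error ≈ 2{1 − Φ[1.96 × 0.25s / 0.0530]}.

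At r = 0.5, s = 0.3 and the rejection threshold is 1.96 × 0.075 = 0.147. Power ≈ Φ(0.003 / 0.0530) = Φ(0.057) = 52%. Error ≈ 2[1 − Φ(2.77)] = 0.6%. Simulation at r = 0.5 gives power of 51% for the independent t and 48% for Mann-Whitney, against 78% for the paired t and about 76% for signed-rank.

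| r | 0 | 0.25 | 0.5 | 0.75 |
|---|---|---|---|---|
| s | 0.212 | 0.245 | 0.300 | 0.424 |
| Power, independent t (normal approximation) | 81% | 71% | 52% | 14% |

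The paired comparison on the same approximation is 81% throughout. There is no loss at r = 0, and 51% is not a lower bound.

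**3. Two device contrasts, both paired, each at 0.05.** Both use night 1. Under the assumptions above, the two differences have covariance s²(1 − r) and variance 2s²(1 − r) each, so their correlation is 0.5 whatever r is. With no effect, 1 − P(|Z₁| < 1.96, |Z₂| < 1.96) = 9.1%, confirmed by simulating paired t tests at n = 32. The range is 9.75% at correlation 0 to 7.0% at 0.9. Each contrast alone keeps 5%.

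**4. Power under candidate rules** (paired t, 32 evaluable, difference 0.15, SD 0.3 per device difference, correlation 0.5 between differences):

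| Rule | Power |
|---|---|
| One paired contrast at 0.05 | 78% |
| Holm, per contrast, both methods work | 74% |
| Holm, only one works | 68% |
| Fixed order, both work | 78% first, 66% second |
| Pooled contrast | 89% if both work, 35% if only one |

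If 0.3 is instead the SD of the pooled difference, the pooled contrast has 78%. Holm holds overall error at 4.0% to 4.9% for correlations from 0.8 down to 0.

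**5. Size needed for 80% at 0.025 each.** [0.3 × (2.241 + 0.842) / 0.15]² = 38.0, so 39 evaluable; 39 / 0.95 = 41.1, so 42 enrolled.

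**The case against.** **The test sentence may be general.** It sits in a paragraph that also covers chi-square and Fisher tests. Student t includes the paired form, and 6.2.4 shows paired intent. This stands: a reader might infer that the plan commits to an independent-samples analysis of its main comparison, and the text does not go that far. It does not rescue Mann-Whitney U, which has no paired form, and no signed-rank or other paired non-parametric test is named anywhere.

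**The 51% depends on an unstated correlation.** This also stands. Section 6.2.4 reports outcome SDs starting at 0.2 ("was 1.4 times with standard deviation of 0.2"). With a single-night SD of 0.2 and r = 0.5, the paired-difference SD is also 0.2, and independent-samples power is about 92% against 98% paired, a small loss. The figure illustrates the mechanism; it does not estimate this trial's power.

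**The 9% needs a success rule that the plan lacks.** A reader might infer that the trial runs at 9% error, or that 5% error and the planned power apply only to a single contrast. Neither follows. No passage says a claim on either device is enough, and each of two paired contrasts separately keeps 5% error and the same power.

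**Temperature may not be co-primary.** Section 6.3.1 lists both quantities among the dependent variables, and the wording in 6.5 is a rough translation. That is a fair reading, so the 9% is confined to energy expenditure.

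**The inputs are provisional.** The pilot is to update the SD, so any restated power must be marked as subject to that update.

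**Conclusion.** The mismatch between a paired sample size and an analysis section that names Mann-Whitney U for same-patient data is an error as written and should be corrected. The unstated pairing of Student t belongs with it. At an assumed between-night correlation of 0.5, with 0.3 as the SD of the paired difference, the cost is roughly 27 points of power for the t test (78% to 51%) and 28 for the rank test (76% to 48%). The cost ranges from nothing at correlation 0 to most of the power at 0.75.

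The undefined contrast is a lesser point, mainly missing detail. It becomes an error-rate question, at about 9%, only if a claim on either device is allowed to count.

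The documents do not support saying that the trial has 51% power or 9% error, or that its enrolment is wrong for this reason. The fixed order of nights is a separate design issue that no choice of test resolves.

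**What to change.** **In 6.5:**
1. Use the paired t test for all between-night comparisons, with Wilcoxon signed-rank in place of Mann-Whitney U.
2. Name resting energy expenditure, the quantity sized in 6.2.4, as the primary outcome and temperature as secondary.
3. Declare either one pooled active-versus-passive contrast at 0.05, or plate versus passive and blanket versus passive. If a claim on either device is to count, apply Holm or a pre-specified fixed order.

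**In 6.2.4:** restate power for the chosen rule from the table above, at 32 evaluable and subject to the pilot SD update.

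**Cost.** Only wording changes, and enrolment can stay at 34. Under Holm, power per contrast is below the planned 80%; restoring it at 0.025 each would take about 42 enrolled, which is not proposed here. A fixed order allows no claim on the second device if the first fails. A pooled contrast supports no claim about a single device and is weak if only one works. Temperature can no longer carry the primary conclusion.

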6.2.3. Sampling design

Sampling in the selection of patients shall be per snowball, all participants in the centre shall be included until sample saturation or until 18 months after the start of the study, in which metabolic expenditure will be assessed in all 3 cases: passive external overheating, thermal plate overheating and convective air blanket overheating.

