6.4.2 Data collection

For the analysis of thermal comfort, the suppliedam biennage temperatureshall be analysed in the values: minimum of 25oC, 28oC, 31oC as shown in Table 6... The ambient temperature of 33oC is obvious, as it is considered that in combination with the elements of active external overheating average conditions of 33oC are reached. The graphical representation of the

Table 6: Scenario of combination analysis of heating methods

	Ambient temperature		
Registration No.	25oC	28oC	31oC
Thermal plate at 50 cm	1	3	5
Thermal plate at 100 cm	2	4	6
Convective air blanket 38oC			
Convective air blanket 43oC			

measures shall be carried out as represented in *Annexess IV* and *V*.

The convective air blanket, by the heating mechanism, an analysis will be carried out, studying the theoretical effect combined with the ambient temperature.

Sociodemographic and nutritional data of the patient will be collected after acceptance and signature of the informed consent that will be collected in the first days after the patient's entry into the burn unit. Variables will be collected during the night shift (22:00 to 8:00) because there are no scheduled tasks of cures, diagnostic tests or surgical intervention that may alter both the care activity in the unit and the alteration of variables to be collected. Data will be collected for 6 hours from the intervention: evolution of body and central temperature and metabolic expenditure calculated in 24 hours. From the third day after the burn, the 3 heating methods will be applied to study, on three consecutive nights

Study Protocol, Statistical Analysis Plan (SAP), Informed Consent Form (ICF). Version 1.0

Night 1: Ambient temperature 32oC

Night 2: Ambient temperature and combination with thermal plate

Night 3: Ambient temperature and combination with thermal blanket.

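### Section 6.5 names no paired test for the heating comparison, and its rank test is for independent groups, although every patient is measured under all three methods and N = 34 is a paired figure

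*Combined protocol and SAP*

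**What the plan says.** **Design.** Section 6.1 describes an "epidemiological study without control group". Section 6.2.3 says that "metabolic expenditure will be assessed in all 3 cases", and section 6.4.2 that "the 3 heating methods will be applied to study, on three consecutive nights". Passive heating is Night 1, the plate is added on Night 2 and the blanket on Night 3.

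**Sample size.** Section 6.2.4 states that the sample size "was calculated for the difference of media coupled in energy expenditure at rest", comparing the combined methods with passive heating. With two-sided alpha 0.05, beta 0.2, SD 0.3 and 5% loss, it concludes that "34 subjects are required to detect a difference equal to or greater than 0.15 units".

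**Analysis.** Section 6.5 says: "A single-rate analysis shall be performed by observing as variables main dependent temperature and metabolic expenditure". The next sentence gives the only tests for quantitative variables: "quantitative variable means will be contrasted using Student t or Mann-Whitney's U-depending on the sample distribution". Chi-square and Fisher tests follow for qualitative variables, then a possible logistic regression. No paired t test, Wilcoxon signed-rank test, Friedman test, repeated-measures ANOVA or mixed model appears.

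**The concern.** The only heating comparison that this design allows is within patients, because there is no separate group of patients for any method. The sample size respects that; the analysis section does not. Mann-Whitney U has no paired form. It is offered as the alternative to the t test for the same contrast, so the pairing of the two names suggests the independent-samples t test as well.

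An independent-samples test treats the readings from two nights as if they came from different people. Its standard error is then wrong whenever a patient's readings are correlated. If the correlation is positive, as one would expect for the same patient on consecutive nights, the test is too conservative, the interval is too wide, and a real effect of the planned size can be missed. If it is negative, the error goes the other way, with slightly too many false positives and intervals slightly too narrow.

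Lost power would be hard to recover here: section 6.2.2 puts thermal-burn admissions in 2018 at 30, and recruitment stops at 18 months.

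**Working it through.** **1. Reproduce N.** Inputs from section 6.2.4: two-sided alpha 0.05 (z = 1.96), power 80% (z = 0.8416), difference 0.15, SD 0.3, loss 5%.

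- Paired: n = (1.96 + 0.8416)² × 0.3² / 0.15² = 31.4, so 32. With loss: 32 / 0.95 = 33.7, so **34**, as stated.
- Independent groups, SD 0.3: n = 2 × 31.4 = 62.8, so 63 per group (63 / 0.95 = 66.3, so 67 with loss). This does not give 34.

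The plan's figure is therefore paired, and it reproduces when 0.3 is read as the SD of the within-patient differences.

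**2. Power with the matching test.** With 32 evaluable patients, the exact power of the paired t test is 78.2%. Wilcoxon signed-rank gives about 76% by simulation.

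**3. Power and error rates if the pairing is ignored.** The correlation r between two nights is needed and is not in the documents, so a range is used. The SD of differences is held at 0.3. Section 6.2.4 reports an increase of "1.4 times with standard deviation of 0.2 - 0.32 times" from studies in burned patients. Reading that SD range as the SD on a single night implies

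r = 1 − 0.3² / (2 × SD²).

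For example, SD 0.30 gives r = 1 − 0.09 / 0.18 = 0.5, and SD 0.20 gives r = 1 − 0.09 / 0.08 = −0.125. Bivariate normal data were simulated with 32 pairs and true difference 0.15 (power) or 0 (type I error), using 40,000 trials per setting for the t tests and 20,000 for the rank tests.

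| Per-night SD | r | Unpaired t: power | Unpaired t: type I error | Coverage of its 95% CI | CI width against paired | Mann-Whitney power |
|---|---|---|---|---|---|---|
| 0.20 | −0.125 | 82% | 6.4% | 93.6% | 7% too narrow | 80% |
| 0.21 | 0 | 79% | 5% | 95.0% | about equal | 77% |
| 0.25 | 0.28 | 68% | 2.2% | 97.9% | 16% too wide | 65% |
| 0.30 | 0.5 | 50% | 0.6% | 99.4% | 39% too wide | 47% |
| 0.32 | 0.56 | 43% | 0.4% | 99.6% | 48% too wide | 40% |

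The paired t test gives 78% power and 5% type I error in every row. The mean CI half-width is 0.107 for the paired analysis throughout, and 0.099, 0.106, 0.124, 0.149 and 0.159 for the unpaired one. Against the paired t test, the change in power runs from 82 − 78 = 4 points gained, with an inflated type I error, to 78 − 43 = 35 points lost.

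**4. Other reading of the SD.** If 0.3 were the SD of a single night's measurement, unpaired power would be about 50% at any correlation. Paired power would be 49% at r = 0, 78% at r = 0.5 and 94% at r = 0.7. The loss again grows with positive correlation.

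**The case against.** The paired t test is also a Student t test, and section 6.2.4 refers to coupled means. Read together, the two sections could mean a paired t test for normal data, leaving a definite error only when the rank test is used. The sentence in 6.5 is also generic. It does not mention the heating methods, and it may have been written for comparisons between patients, such as by sex or beta-blocker use, where Mann-Whitney is suitable. The text reads as a translation, so a word for paired may have been lost.

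The ambiguity about the t test is real, and the point does not depend on resolving it. If the sentence covers the heating comparison, the rank test is wrong and the form of the t test is open. If it does not, the main comparison has no test at all. Both cases need the same correction.

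It is also fair to say that the table rests on two readings that the plan does not state: 0.3 as the SD of differences, and 0.2 to 0.32 as a per-night SD. The power figures illustrate a range; they are not a forecast. Under positive correlation the error is conservative, so the main risk is a missed effect and not a false claim. Data collection is unaffected, so the plan can be corrected before analysis.

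A paired test does not settle which contrast is primary, multiplicity over two contrasts and two main variables, how temperature over six hours is summarised, or the fixed order of methods by night. Those are separate questions and do not weaken this one.

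**Conclusion.** The concern holds and must be fixed. The design and the sample size are paired, while section 6.5 names no paired method and offers a rank test for independent groups. That part is certain from the text and from the reproduction of N = 34.

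The size of the harm depends on the unknown within-patient correlation. An unpaired analysis could leave power almost unchanged when the correlation is near zero, or bring it to about 43% (t test) or 40% (Mann-Whitney) at r = 0.56. These figures assume 32 evaluable patients, normal data, a true difference of 0.15 and an SD of differences of 0.3. Only at zero correlation would the unpaired p-values and intervals be right. Positive correlation is expected, so lost power and intervals that are too wide are the likely result.

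**What to change.** Add to section 6.5, for example:

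> Energy expenditure and temperature under each active heating method will be compared with passive heating in the same patients by paired t test, or by Wilcoxon signed-rank test if the within-patient differences are not normally distributed. The mean or median within-patient difference will be given with its 95% CI. Independent t, Mann-Whitney, chi-square and Fisher tests will be used only for comparisons between groups of patients.

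The normality check should be made on the within-patient differences, not on each night's values. A linear mixed model with heating method as a fixed effect and patient as a random intercept is an acceptable alternative.

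The cost is one or two sentences. No extra patients or data are needed, and the tests are standard in the named software. N need not change for this point, though the exact paired t power with 32 evaluable patients is 78%, slightly below the nominal 80%; with all 34 evaluable it is 81%.

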6.3.1. Dependent variables

At the stage of defining thermal comfort, the variables shall be collected:

- Operating temperature (Dry temperature + radiant temperature)
- Relative humidity
- Air speed

For the assessment of nutritional data and energy expenditure, the variables will be collected: Weight, Height, Ideal Weight, BMI (kg/m²), FiO₂, Charlson Index, Nutri- Score, Nutritional Biochemistry, Serum Albumin (g/dl). The calculation of theoretical caloric requirements (kcal/day) using the Penn State predictive formula and the protein requirements/day (gr/day) calculation will be included.

- Metabolic expenditure, calculated by Indirect calorimetry collecting the variables:
 - VCO₂: Carbon dioxide production (Avg VCO₂, VCO₂ hp)
 - VO₂: Consumption of O₂ (Avg VO₂, VO₂ HP)
 - o RQ: Cociente respiratorio (Avg RQ, Avg EE)
 - EE: Energy expenditure in kcal/d (Avg EE/m², AVG EE/Kg)
- Body temperature via surface thermometer
- Central temperature recorded by bladder probethermometer, from entry and registration c/8h until 7 days after admission. Time recording of temperature during heating analysis.
- Calculation of liquid loss estimation.

The difference of the metabolic state at rest versus the actual one will be categorized by qualitative scale.

Due to the critical condition of the patient, the CONFORT scale will be collected for the evaluation of sedation and pain in the critical patient.

For the assessment of the comfort status (NOC 2008) and thermoregulation (NOC 0800) according to Thert scale will be carried out in the application of the two heating techniques.

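### Section 6.5 offers only Chi-square and Fisher for qualitative outcomes, although each patient is observed under two or three heating methods, so a category-by-method comparison would ignore the pairing and any order of the levels.

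*Combined protocol and SAP*

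**What the plan says.** Section 6.5 has two testing rules. Means of quantitative variables go to Student t or Mann-Whitney U. For the rest: "The Chi-square test for contingency tables and the Fisher test will be used to assess association of qualitative variables". No paired or ordinal method for categories is named. The logistic regression is optional, and no repeated-measures structure is given for it.

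Section 6.3.1 creates at least one outcome under the second rule: "The difference of the metabolic state at rest versus the actual one will be categorized by qualitative scale". It also has comfort and thermoregulation scored, "according to Thert scale will be carried out in the application of the two heating techniques", without saying whether those scores are qualitative or quantitative. No number or order of levels is given for any of these.

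The design is within-patient. Section 6.2.3 states that "metabolic expenditure will be assessed in all 3 cases", and section 6.4.2 places the three methods on three consecutive nights in the same patient. Section 6.2.4 sizes the study on a paired difference in means.

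**The concern.** Pearson's Chi-square and Fisher's exact test assume that each entry in the table is an independent person. With 32 evaluable patients, a table of category by heating method holds 64 entries for two methods or 96 for three, all from the same 32 people. Both tests also treat levels as unordered labels, so a consistent one-step shift is spread over several degrees of freedom.

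The p-values would be wrong and, with positively correlated nights, too large. A real difference between methods on these outcomes could be reported as no association. Making the Student t and Mann-Whitney rule paired would not help, because the rule for qualitative variables is a separate sentence.

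**Working it through.** **Inputs from section 6.2.4.** The calculation uses a two-sided alpha of 0.05, power of 0.80, an SD of 0.3 and 5% loss to follow-up, and its result is that "34 subjects are required to detect a difference equal to or greater than 0.15 units".

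**Step 1: reproduce the plan's figure.** For paired means, n = (SD × (z0.975 + z0.80) / difference)² = (0.3 × 2.802 / 0.15)² = 31.4, rounded up to 32. Allowing for loss, 32 / 0.95 = 33.7, rounded up to 34. This matches. It works only if 0.3 is the SD of the within-patient difference, so the plan relies on pairing.

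**Step 2: direction of the error.** For a single category with probability p on each of two nights, and correlation r between a patient's two indicators, the difference in proportions has variance 2p(1 − p)(1 − r)/n. The unpaired test uses 2p(1 − p)/n. With r above 0 it overstates the variance and rejects too seldom.

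**Step 3: size of the error.** The plan gives no sizing for these scales, so this part is simulated under assumptions: 32 patients; latent normal scores cut into 3 or 5 equally likely ordered levels; within-patient correlation 0 to 0.8; 1,500 replicates per setting (Monte Carlo standard error at most √(0.25/1500) = 1.3 points). The reference shift is 0.5 latent SD. At correlation 0.5 the SD of the paired difference is √(2 × (1 − 0.5)) = 1 latent SD, so this shift equals the plan's 0.15/0.3 = 0.5, borrowed from energy expenditure.

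Power for two methods, Chi-square against Wilcoxon signed-rank, with relative loss:

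| Correlation | Shift (SD) | 5 levels | Loss | 3 levels | Loss |
|---|---|---|---|---|---|
| 0 | 0.5 | 28.1% vs 43.7% | 36% | 31.9% vs 38.1% | 16% |
| 0.3 | 0.5 | 22.7% vs 55.5% | 59% | 30.1% vs 48.3% | 38% |
| 0.5 | 0.5 | 20.1% vs 67.1% | 70% | 27.4% vs 59.0% | 54% |
| 0.7 | 0.5 | 18.3% vs 86.3% | 79% | 25.3% vs 74.5% | 66% |
| 0.8 | 0.5 | 14.4% vs 94.0% | 85% | 22.9% vs 85.8% | 73% |
| 0.5 | 0.7 | 48.6% vs 91.9% | 47% | 60.0% vs 86.7% | 31% |

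Loss is (paired − Chi-square) / paired; for example (67.1 − 20.1) / 67.1 = 70%.

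**Step 4: separate order from pairing.** With five levels, correlation 0.5 and shift 0.5 SD, Mann-Whitney U, which keeps the order but not the pairing, has 42.7% power. Power thus goes from 20.1% to 42.7% by using the order, and to 67.1% by also using the pairing.

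**Step 5: three nights.** At correlation 0.5 and shift 0.5 SD on both active nights, Chi-square against Friedman gives 17.6% vs 67.9% with five levels and 25.3% vs 59.3% with three.

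**Step 6: type I error.** With no true shift, the nominal 5% Chi-square test rejects in 3.5% of runs at correlation 0.3, 2.4% to 2.6% at 0.5 and 1.8% to 2.3% at 0.7 for two methods. For three nights the figures are 2.9% to 3.3%, 1.8% to 2.4% and 0.9% to 1.5%. Overall that is about 1% to 3.5%.

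**The case against.** A reader might infer that section 6.5 sends the comfort and thermoregulation scores to Chi-square or Fisher. The documents do not say so. Section 6.3.1 uses the word qualitative only for the metabolic-state category, and a numeric score could fall under the quantitative rule. In that case order is kept and only pairing is in question: Mann-Whitney U is unpaired, and Student t is not stated to be paired. This objection stands, so those scores are included here only conditionally.

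Order is also assumed for the metabolic-state category. Its levels are not listed, and with two levels the point about order disappears. The point about counting patients more than once does not.

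The effect on the study is limited. The category is derived from energy expenditure, which is analysed in its own right. Section 6.5 names temperature and metabolic expenditure as the main dependent variables and promises no between-method test of these scales. The sentence on Chi-square and Fisher is generic and suits variables recorded once per patient, such as sex or origin of the burn. All of this lowers the weight of the point. Even so, anyone comparing a category across methods under this SAP has no valid test named for it.

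**Conclusion.** The point holds as a secondary matter that should be corrected. The only rule given for qualitative variables does not fit a design in which each patient contributes two or three observations. This is clear for the metabolic-state category compared across heating methods, and follows for comfort and thermoregulation if they are treated as qualitative.

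Two stronger readings are not supported. One is that most of the power is always lost. In the simulations the loss exceeds half when nights correlate at about 0.5 or more and the shift is about half an SD. It is 16% to 36% at zero correlation and 31% to 47% at correlation 0.5 with a 0.7 SD shift. The documents give no correlation, level count or effect for these scales, so no single figure can be claimed. The other is that false positives would rise. With positive correlation the test rejects less often than 5%, so the harm is missed differences.

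**What to change.** In section 6.5:

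- Limit Chi-square and Fisher to characteristics recorded once per patient.
- For any graded scale rated under more than one heating method, use the Wilcoxon signed-rank test for two methods or Friedman for three, and report how many patients improved, stayed the same or worsened.
- For a two-level category, use McNemar for two methods or Cochran's Q for three.

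In section 6.3.1, state for the metabolic-state category and for the comfort and thermoregulation scores the levels, their order, and whether each is analysed as qualitative or quantitative.

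The cost is a few sentences of wording. No new data, patients or software are needed; the named package has all of these tests.
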